### 2.8.3.2 Vital signs

The following quantitative variables will be summarized: Weight (kg), Temperature (°C), Pulse (beats/min), Supine systolic blood pressure (mmHg) and Supine diastolic blood pressure (mmHg).

Analysis in vital sign measurement using descriptive summary statistics for the change from baseline for each post-baseline visit will be performed by vital sign and treatment group. Change from baseline will only be summarized for patients with both baseline and post-baseline values and will be calculated as:

$$\text{Change from baseline} = \text{post-baseline value} - \text{baseline value}$$

The number and percentage of patients with newly occurring notable vital signs will be presented. Criteria for notable vital sign abnormalities are provided in [Table 2-3](#) below.

**Table 2-3 Criteria for notable vital sign abnormalities**

Vital sign (unit)	Notable abnormalities
Systolic blood pressure (mmHg)	$\geq 180$ mmHg/ $\leq 90$ mmHg with increase/decrease from baseline of $\geq 20$ mmHg
Diastolic blood pressure (mmHg)	$\geq 105$ mmHg/ $\leq 50$ mmHg with increase/decrease from baseline of $\geq 15$ mmHg
Pulse (beats/min)	$\geq 120$ bpm/ $\leq 50$ bpm with increase/decrease from baseline of $\geq 15$ bpm
Temperature (°C)	$\geq 37.5$ (axillary) or $\geq 38.0$ (other routes)
Weight	decrease > 7% from baseline increase > 7% from baseline

[figure not shown]
A listing of all newly occurring or worsening abnormalities will be provided, as well as a by-patient listing of all vital signs.

## 2.9 Pharmacokinetic endpoints

PK concentrations below the limit of quantification will be treated as zero in summary statistics and for the calculation of pharmacokinetic parameters by non-compartmental method of analysis. Descriptive statistics of pharmacokinetic parameters will include arithmetic and geometric (means, standard deviation (SD), median, minimum and maximum, etc). Parameters such as AUCinf, AUClast, AUC0-t, Cmax, T1/2 and Tmax will be reported

[figure not shown]
[figure not shown]
using non-compartmental method of analysis (using Phoenix 6.4 or higher). 2-sided 90% confidence intervals for  $AUC_{0-24h}$ ,  $C_{max}$  and  $T_{max}$  PK parameters of KAE609 and Lumefantrine will be calculated by cohort and treatment group using normal or log-normal approximation as applicable.

[figure not shown]
All the PK data may be pooled for population pharmacokinetics analysis and the broad principles outlined in the Food and Drug Administration (FDA) Guidance for Industry: Population Pharmacokinetics would be followed.

[figure not shown]

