An abbreviated physical examination will be performed at all other visits starting from Study Day 1. An abbreviated physical exam will include the examination of general appearance, vital signs (blood pressure and pulse) and body temperature. Fever monitoring will be done until resolution of fever, defined as being afebrile for 48 hours.

Body weight will also be measured at Study End (Study Day 29 or earlier in case of premature patient discontinuation) and data recorded on clinical data base.

⁵ Laboratory tests should also be taken at any time of withdrawal/discontinuation.

⁶ Missed PK sampling time should be taken as soon as possible and actual time should be recorded. **For Scheduled time ≤ 2 h \pm 10 min; 2 - ≤ 24 h \pm 30 min; > 24 - ≤ 72 \pm 2 h, > 72 h \pm 24 h.**

⁷ Will be repeated in case of abnormalities.

⁸ The patient's menstrual and contraceptive history will be taken and a serum/plasma β -hCG pregnancy test will be performed at screening to exclude pregnancy. A urine β -hCG test will be performed at end of study. Results must confirm negative **before** dosing.

⁹ Meals consumed within 30 min prior to dosing and 4 hours post dosing to be documented for Coartem cohort.

¹⁰ Comparator only (Coartem).

¹¹ Not applicable to 1-day treatment regimen.

¹² ECG's should be taken in triplicate within 5 min after resting for at least 10 min in the supine position to ensure a stable heart rate according to the ECG investigator manual. Also, ECG's should be taken before any other procedure taken at the same nominal time point is performed. **For Scheduled time ≤ 2 h \pm 10 min; 2 - ≤ 24 h \pm 30 min; > 24 - ≤ 72 \pm 2 h, > 72 h \pm 24 h.**

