**Figure 1-1 Study KAE609A2202 diagram**

Given the expected sub-therapeutic efficacy of the doses of KAE609 in the first 2 cohorts, a smaller number (N=10) of patients will be included (10 mg Single Dose (SD), 25 mg SD and 10 mg 3 Days) to detect potential LFT increases. In the subsequent cohorts a higher number (N=20) of patients will be included. All patients will be followed up for 4 weeks with close monitoring in an inpatient setting for at least the first 3 days (Study Day 4) for efficacy and safety followed by outpatient monitoring up to Study Day 29.

Patients will be randomized to KAE609 vs Coartem in a ratio of 1:1 in cohort 1. In cohort 2, SD KAE vs QD KAE609 vs Coartem will be randomized in the ratio of 1:1:1. In Cohorts 3

and 4 the SD KAE609 vs QD KAE609 vs Coartem will be randomized in the ratio of 2:2:1. In Cohorts 5 and 6 the SD KAE609 vs Coartem will be randomized in the ratio 2:1. There are no stratification factors in this study.

Visits to assess safety and efficacy will be scheduled during the follow-up period as described in the assessment schedule table in protocol.

The safety of entire study will be monitored by the Safety Review Committee.

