## 1.2 Study objectives and endpoints

**Table 1-2 Objectives and related endpoints**

Objective(s)	Endpoint(s)

Primary Objective(s)
 
 
To characterize hepatic safety aspects of single- and multiple ascending doses of KAE609 in adult malaria patients
 
	
Endpoint(s) for primary objective(s)
 
 
At least 2 CTCAE grades increase from baseline in ALT or AST during the 4 week study period
 

Secondary Objective(s)
 
 
To evaluate overall safety and tolerability of KAE609.
 
To assess key PK parameters following treatment with KAE609.
 
To assess the efficacy of KAE609 in patients with uncomplicated falciparum malaria.
 
To assess recrudescence after single and multiple doses of KAE609
 
	
Endpoint(s) for secondary objective(s)
 
 
Standard safety/tolerability assessments (AE incidence and severity, vital signs, ECG, laboratory abnormalities)
 
PK parameters such as AUC, Cmax, Tmax, T1/2 etc.
 
PCR-Uncorrected adequate clinical and parasitological response (ACPR) and PCR-Corrected ACPR at Days 15 and 29 (i.e., 14 and 28 days post-dose)
 
Parasite and Fever Clearance Times (PCT and FCT) before rescue medication is given
 
Incidence rate of recrudescence at Day 29
 

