**Table 5-6 Analysis visit windows based on study day and time**

Analysis Visit	Analysis timepoint	Analysis window for assessment group			
		Temperature/ Parasite count	ECG		PK
			KAE609	Coartem	
Baseline	0 hrs	up to 0 hrs	up to < 0 hrs	up to < 0 hrs	NA
Day 1	1 hrs	NA	NA	NA	>0 to 1.5 hrs
	2 hrs	>0 to 3 hrs	NA	NA	>1.5 to 3 hrs
	4 hrs	>3 to 6 hrs	>0 to 8 hrs	NA	>3 to 5 hrs
	6 hrs	NA	NA	>0 to 37 hrs	>5 to 7 hrs
	8 hrs	>6 to 10 hrs	NA	NA	>7to 10 hrs
	12 hrs	>10 to 18 hrs	>8 to 18 hrs	NA	>10 to 18 hrs
Day 2	24 hrs	>18 to 30 hrs	>18 to 38 hrs	NA	>18 to 38 hrs
	36 hrs	>30 to 42 hrs	NA	NA	NA
Day 3	48 hrs	>42 to 54 hrs	NA	NA	>38 to 49 hrs

	50 hrs	NA	NA	NA	>49 to 51 hrs
	52 hrs	NA	>38 to 56 hrs	NA	>51 to 54 hrs
	56 hrs	NA	NA	NA	>54 to 58 hrs
	60 hrs	>54 to 66 hrs	>56 to 66 hrs	NA	>58 to 64 hrs
	68 hrs	NA	NA	>37 hrs to Day13	>64 to 70 hrs
Day 4	72 hrs	>66 hrs to Day 4	>66 hrs to Day 16	NA	>70 hrs to Day 6
Day 5	NA	Day 5-6	NA	NA	NA
Day 8	NA	Day 7 – 9	NA	NA	Day 7 – 9
Day 11	NA	Day 10 – 13	NA	NA	NA
Day 15	NA	Day 14 – 16	NA	NA	NA
Day 22	NA	Day 17 – 25	NA	NA	NA
Day 29/end of study	NA	Day 26 and above	Day 17 and above	Day 14 and above	NA

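### SAP 2.9 gives Tmax the same parametric 90% interval as AUC0-24h and Cmax, and in arms of 10 to 20 its coverage is not assured

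*SAP*

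**What the plan says.** Tmax is a listed secondary PK endpoint (SAP Table 1-2: "PK parameters such as AUC, Cmax, Tmax"). SAP 2.9 derives the parameters by a non-compartmental method and plans descriptive statistics for them, including "median, minimum and maximum, etc". It then adds "2-sided 90% confidence intervals for" AUC0-24h, Cmax and Tmax of KAE609 and lumefantrine, which "will be calculated by cohort and treatment group using normal or log-normal approximation as applicable". It does not say whether Tmax is handled on the raw or log scale, whether the quantile is t or z, or after which dose Tmax is taken. Protocol 9.5.4 plans descriptive PK statistics only, with no interval.

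SAP Table 5-6 ("Analysis visit windows based on study day and time") lists PK time points at 1, 2, 4, 6, 8, 12 and 24 h, then 48, 50, 52, 56, 60, 68 and 72 h, and Day 8. Footnote 6 to the Protocol's assessment schedule allows ±10 min up to 2 h, ±30 min up to 24 h and ±2 h up to 72 h. It adds: "Missed PK sampling time should be taken as soon as possible and actual time should be recorded".

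On arm sizes, SAP 1.1 says that for the KAE609 arms of Cohorts 1 and 2 "a smaller number (N=10) of patients will be included". It continues: "In the subsequent cohorts a higher number (N=20) of patients will be included". Coartem totals 60 over six cohorts (SAP 3.2), about 10 per cohort.

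**The concern.** A normal or log-normal interval is natural for AUC0-24h and Cmax, which are continuous. Tmax differs, because non-compartmental Tmax is the clock time of a blood sample. Several patients in an arm will share a value or nearly so, and one late value can move the mean and standard deviation of a 10-patient arm a long way. If every patient peaks at the same recorded time, the interval has zero width.

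At stake is the accuracy of a reported interval for a secondary PK parameter. The choice left open by the closing words of the SAP sentence also matters, because the result depends on scale and quantile.

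**Working it through.** **Inputs.** Level: 90%, two-sided (SAP 2.9). Arm sizes: 10 and 20 (SAP 1.1). Grid: 1, 2, 4, 6, 8, 12, 24 h (SAP Table 5-6). The distribution of Tmax on that grid is not in the documents and is assumed below, over a range. The interval is mean ± q × SD/√n, raw or log, with q from t(n−1) unless stated. Coverage is judged against the true mean on the same scale.

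**Benchmark.** The plan states only the nominal 90%. On continuous log-normal data, the log-scale t interval covers 89.8-90.0% in simulation at n=10, 20 and 60, so the method delivers its level where its assumptions hold.

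**Tmax spread over several times.** Take a log-normal true Tmax with median 3-6 h and CV 30-80%, placed on the grid. The log-scale t interval covers 88.9-90.4% at n=10 and 89.4-90.2% at n=20. Grouping into sampling times alone does little harm.

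**Skewed Tmax, raw scale.** Put 20, 35, 25, 8, 5, 2 and 5% of patients on the seven times in order (200,000 simulated arms). The raw-scale t interval covers 72% at n=10 and 77% at n=20, while the log-scale interval covers 90% at both sizes. Milder skewness gives 82-84% on the raw scale. The raw-scale loss is largely skewness: continuous log-normal data with CV 80% give 84.5% at n=10.

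**t or z.** On continuous log-normal data at n=10, z in place of t lowers log-scale coverage from 90.0% to 86.5%.

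**Concentrated Tmax with a late peak, exact.** Assume 90% of patients at 4 h and 10% at 24 h. The true mean is 0.9×4 + 0.1×24 = 6 h. Let K be the number at 24 h in an arm of 10, so K is Binomial(10, 0.1). The arm mean is 4 + 2K and SD = 20√[K(10−K)/90]. The half-width is 1.833 × SD/√10.

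| K | Probability | Interval (h) | Covers 6 h? |
|---|---|---|---|
| 0 | 0.349 | 4 to 4 | no |
| 1 | 0.387 | 2.3 to 9.7 | yes |
| 2 | 0.194 | 3.1 to 12.9 | yes |
| 3 | 0.057 | 4.4 to 15.6 | yes |
| 4 or more | 0.013 | starts above 6 | no |

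Coverage is 0.387 + 0.194 + 0.057 = 0.638, or 64%; the log scale gives the same. At n=20 the interval covers for K = 1 to 5, and coverage is 86.7%. Spreading the times within the Protocol's sampling windows leaves the n=10 figure at 64%.

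**Almost everyone at one time.** With 95% at 4 h and 5% at 6 h, all values coincide with probability 0.95^10 = 60% at n=10 and 0.95^20 = 36% at n=20. Coverage is 39.8% and 63.8%. Here the windows matter: spreading times within them raises coverage to 85-88% at n=10 and 84-87% at n=20.

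**Multiple-dose arms.** If Tmax is taken over 0-72 h and 5-10% of patients peak on Day 1 (assumed), coverage is 40-75% at n=10 and 64-86% at n=20.

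**Distribution-free alternative.** The interval from the k-th smallest to the k-th largest value covers the median with probability at least 1 − 2·P(Bin(n, ½) ≤ k−1), ties included.
- n=10, ranks 2-9: 1 − 2×11/1024 = 97.9%. Ranks 3-8: 1 − 2×56/1024 = 89.1%, below 90%.
- n=20, ranks 6-15: 95.9%. Ranks 7-14: 88.5%, below 90%.

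**The case against.** An approximate interval for a mean does not require continuous data. On the SAP's own grid the log-scale t interval is within about one point of nominal for a plausible spread of values. The poor figures come from assumed concentrated, two-peak or skewed distributions, and no document says Tmax behaves that way. The wording on approximation would let the analyst choose the log scale. **This stands**, and it limits the point to coverage that is not assured.

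Tmax is also not strictly confined to the scheduled times. Windows apply, actual times are recorded at least for missed samples, and the SAP does not say that nominal times enter the calculation. Table 5-6 defines analysis windows and does not separate KAE609 from Coartem for PK, so the grid for each arm is an inference. **This stands in part**: the windows repair much of the case with 95% at one time, but not the case with 10% at 24 h.

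The median and range are already planned, SAP Table 2-5 plans no graph of PK parameters, and nothing is decided on the Tmax interval. **This stands** and keeps the point minor.

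A reader might go further and infer that, because Tmax is discrete, these intervals simply do not have 90% coverage. The log-scale results contradict that. A reader might also test the interval against the median and find very low coverage, but the SAP never says that the interval estimates the median.

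**Conclusion.** The point holds in a limited form. SAP 2.9 applies a normal or log-normal 90% interval to a clustered variable in arms of 10 to 20 and leaves scale, quantile and dosing interval open, so the nominal level is not assured. Under assumed distributions on the first-24-hour grid, coverage of the mean runs from about 90% (log scale, values spread) to about 72-84% (raw scale, skewed) and about 64% at n=10 (90% at 4 h, 10% at 24 h). The more extreme figures need nearly all patients at one exact time, or a single Tmax taken across several doses.

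The documents support neither a claim that coverage will fail nor a claim that dose escalation or the primary analysis is affected. Escalation rests on ALT/AST criteria and committee review, and the primary analysis uses Clopper-Pearson intervals and Fisher's exact test. The change is worth making because it costs little.

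**What to change.** In SAP 2.9:
- Restrict the parametric 90% interval to AUC0-24h and Cmax, on the log scale.
- For Tmax, report the median, minimum and maximum already planned. If an interval is kept, use the order-statistic interval for the median, choosing the narrowest symmetric ranks with at least 90% coverage at the number actually evaluable in the PK analysis set. That is ranks 2-9 of 10 (at least 97.9%) or 6-15 of 20 (at least 95.9%). With 9 evaluable, ranks 2-8 give 1 − 2×10/512 = 96.1%.
- State the dosing interval to which Tmax refers in the 3-day KAE609 and Coartem arms, for example after the first and after the last sampled dose separately.

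The cost is a sentence or two in the SAP and a small change to the PK table program. The downside is that the median interval is conservative at these sample sizes, so it will be wider than an exact 90% interval would be. No decision rule changes.

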## **2.11 Patient-reported outcomes**

NA.

## **2.14 Overview of analysis methods**

An overview of statistical analyses and methods applied to efficacy variables and safety variables are given in [Table 2-4](#) and [Table 2-5](#).

**Table 2-4 Overview of analysis methods for baseline data and efficacy variables**

Variable(s)	Summary statistics for binary/ categorical data	Listings	95% CI for each treatment group	Summary statistics for continuous data	Time-to-event data analysis K-M	Graphs
Medical history	X	X	-	-	-	-
Demographics and baseline characteristics	X	X	-	X	-	-
Patient disposition	X	X	-	-	-	-
Prior medication use	X	X	-	-	-	-
Concomitant medication use	X	X	-	-	-	-
Concomitant rescue medication use	X	X	-	-	-	-
Non-study drug antimalarial medication use	X	X	-	-	-	-
Prior other prohibited medications use	X	X	-	-	-	-
Concomitant other prohibited medications use	X	X	-	-	-	-
PCR-corrected ACPR response at Days 15 and 29	X	X	X	-	-	-
PCR -uncorrected ACPR response at Days 15 and 29	X	X	X	-	-	-
Proportion of patients with parasitaemia at 12, 24, and 48 hours after treatment;	X	X	X	-	-	-
Time to parasite clearance (PCT)	-	X	-	-	X	X
Time to fever clearance (FCT)	-	X	-	-	X	X
Proportion of patients with early treatment failure	X	X	X	-	-	-
Proportion of patients with late clinical failure	X	X	X	-	-	-
Proportion of patients with late parasitological failure (LPF)	X	X	X	-	-	-

Variable(s)	Summary statistics for binary/categorical data	Listings	95% CI for each treatment group	Summary statistics for continuous data	Time-to-event data analysis K-M	Graphs
Incidence rate of recrudescence at Days 29.	X	-	-	-	X	X
Incidence rate of reinfection at Days 29	X	-	-	-	X	X

**Table 2-5 Overview of analysis methods for safety/PK variables**

Variable(s)	Summary statistics for binary/ categorical data	Listings	Summary statistics for continuous data	Graphs	Between treatment comparison
At least 2 CTCAE grades increase from baseline in ALT or AST	X	X	-	-	X*
AE	X	X	-	-	-
SAE	X	X	-	-	-
severe malaria	X	X	-	-	-
Adverse events of special interest	X	X	-	-	-
Hematology change from baseline	-	X	X	-	-
Clinical chemistry change from baseline	-	X	X	-	-
Liver abnormalities	X	X	-	X 	-
ECG change from baseline	-	X	X	X 	-
ECG abnormality	X	X	-	-	-
Vital signs change from baseline	-	X	X	-	-
Notable vital signs abnormality	X	X	-	-	-
Drug concentrations	-	X	X	X 	-
PK parameters		X	X		

\* For comparison with pooled Coartem. 95% confidence interval will be provided.

 eDISH and mDISH plot.

 Spaghetti plot.

 Time vs Concentration line plot.

## 2.15 Interim safety review

Safety laboratory data and adverse events will be monitored continuously throughout the study using data management’s data review reports.

If there are no significant LFT elevations observed in a cohort at Day 15 (see [Table 1-1](#)), the next cohort with escalated KAE609 doses will start after informing the safety review committee about the findings.

If any significant LFT elevation is observed at Day 15 in any patient(s) in a cohort (see [Table 1-1](#)), a comprehensive safety data review will be performed after all the patients in the cohort have been followed up for 28 days post-treatment.

The safety review committee can pause recruitment and trigger safety review any time based on safety signals. An earlier review of the safety data by the safety review committee/Novartis in the middle of a cohort would be initiated based on occurrences of LFT elevations in the cohort as specified below:

- The number of patients meeting the primary safety endpoint in a treatment arm is at least 2 in Cohorts 1 and 2 or at least 3 in Cohorts 3, 4, 5 and 6.

Data management's data review reports will be provided to the safety review committee and the appropriate Novartis relevant internal and external people who will make decision about whether a KAE609 dosage regimen is safe and can be escalated to the higher dosage. Although the randomization data are not included in the data management system, the study drug (KAE609 QD 1 day, KAE609 QD 3 days, Coartem) and dosage taken by each patient is available in the dosage records. No formal interim safety analysis by treatment group will be performed.

In case that more comprehensive safety analyses by treatment group are needed at the end of cohort or in the middle of cohort, formal interim safety analyses of selected safety or efficacy parameters by treatment group will be provided as described in the safety review charter.

Below is the outline of the data required for the SRM review.

**Table 2-6 Specification of data outputs for SRM data review**

Output	Analysis set	Periodic safety review
Baseline		
Demographic characteristics	FAS	Yes
Background disease characteristics	FAS	Yes
Safety		
Concomitant medications/significant non-drug therapies	Safety	Yes
Relevant medical history/current medical condition	Safety	
All adverse events and Serious adverse events	Safety	Yes
Newly occurring liver enzyme abnormalities (categorical analysis)	Safety	Yes
Clinical chemistry shift table based on CTC grade	Safety	Yes
ALT & AST meeting specified criteria during first 2 weeks	Safety	Yes
eDISH and mDISH plots	Safety	Yes

### 3 Sample size calculation

The incidence of patients experiencing at least 2 CTC grade increase from baseline in ALT or AST is not consistent among KAE609 patient/human challenge studies:

- 3 out of 8 (37.5%) patients in a Study with KAE609 at 10 mg QD.
- 4 out of 11 (36.4%) in a Study with KAE609 at 75 mg QD.
- 1 out of 25 (4%) in a Study with KAE609 at 10 to 30 mg QD.
- 1 out of 21 (4.8%) in a study with KAE609 at 30 mg QD X3.

[figure not shown]
### 3.1 Single arm approach

Figure 3-1 and 3-2 present the probability of observing at least 2 and 3 safety events, respectively, in a treatment group by various sample sizes and true event rates to assess the operational characteristics for the proposed sample sizes.

[figure not shown]
Given the proposed sample sizes in the treatment groups within each cohort, the probability of observing at least 2 safety events in 10 patients or 3 safety events in 20 patients is at least 80% if the true event rate is  $\geq 30\%$  and less than 5% if the true event rate is  $\leq 3\%$ . Specifically:

- For a sample size of 10 patients per treatment group, the probability of observing  $\geq 2$  safety events is greater than 80% if the true event rate is  $\geq 30\%$  and less than 5% if the true event rate is  $\leq 3\%$  (Figure 3-1).
- For a sample size of 20 patients per treatment group, the probability of observing  $\geq 3$  safety events is greater than 90% if the true event rate is  $\geq 30\%$  and less than 5% if the true event rate is  $\leq 3\%$  (Figure 3-2).

**Figure 3-1 Probability of observing at least 2 safety events by sample size and true event rate**

**Figure 3-2 Probability of observing at least 3 safety events by sample size and true event rate**

### 3.2 Power for comparison of KAE609 with Coartem

The comparison between KAE609 doses/regimen with Coartem will help interpretation of liver enzyme elevations in the individual KAE609 treatment arms. In the Pyramax Phase II/III trials ([EMA 2012](#)), the incidence of patients experiencing Grade 2 ALT was 3.4%, which was higher than other comparators including Coartem. The incidence rate of adults and adolescents experiencing at least 2 CTC grade increase from baseline in ALT or AST in Coartem is about 3%. To assess the power for between treatment comparisons, a Coartem incidence rate of 5% is also considered.

**Table 3-1 Power for comparison with Coartem based on 2-sided Fisher exact test**

KAE609 true incidence rate	Coartem® true incidence rate	n for KAE609	N for Coartem®	Power for 2-sided testing		
				5% level	10% level	20% level
50%	3%	10	10	50%	70%	77%
		10	20	86%	91%	95%
		10	30	91%	95%	97%
		10	40	94%	97%	99%
		10	50	93%	97%	99%
50%	3%	10	60	94%	98%	99%
		20	10	78%	84%	92%

		20	20	94%	97%	99%
		20	30	99%	99%	>99%
		20	40	99%	>99%	>99%
		20	50	>99%	>99%	>99%
		20	60	>99%	>99%	>99%
50%	5%	10	10	43%	63%	72%
		10	20	80%	86%	92%
		10	30	85%	92%	95%
		10	40	90%	94%	97%
		10	50	89%	94%	97%
		10	60	90%	95%	97%
50%	5%	20	10	71%	77%	86%
		20	20	89%	94%	97%
		20	30	96%	98%	99%
		20	40	98%	99%	>99%
		20	50	99%	99%	>99%
		20	60	99%	99%	>99%
40%	3%	10	10	28%	50%	54%
		10	20	70%	78%	87%
		10	30	77%	87%	91%
		10	40	84%	91%	95%
		10	50	82%	90%	95%
		10	60	83%	92%	95%
40%	3%	20	10	49%	61%	80%
		20	20	81%	88%	94%
		20	30	93%	94%	98%
		20	40	96%	97%	99%
		20	50	96%	98%	99%
		20	60	98%	99%	99%
40%	5%	10	10	23%	43%	50%
		10	20	61%	71%	81%
		10	30	69%	80%	86%
		10	40	77%	85%	91%
		10	50	73%	84%	92%
		10	60	76%	87%	91%
40%	5%	20	10	43%	53%	71%
		20	20	72%	81%	89%
		20	30	86%	90%	95%
		20	40	91%	93%	97%
		20	50	93%	95%	98%
		20	60	94%	96%	98%

Based on PASS 2011

Given the sample size of 10 to 20 per arm within a cohort, the power to detect treatment difference is low even with large treatment differences using a 2-sided statistical significance

level of 5%. If the true rate is 50% for KAE609 and 3% for the Coartem, the power to detect between treatment difference is about 80% using a 2-sided test at the 20% significance level for n= 10 per arm or at the 10% significance level for n= 20 for KAE609 and 10 for Coartem.

If there are at least 2 cohorts at the end of study and the patients treated with Coartem are pooled from all cohorts, the power to detect treatment difference is greatly increased. In case that the study proceeds to the end with 4 cohorts for a total of 40 patients treated with Coartem, the power to detect treatment difference using 2-sided test at the 5% significance level is 77% and 91% for n=10 and 20 patients treated with KAE609, respectively, if the true rate is 40% for KAE609 and 5% for the Coartem. In case that the study proceed to the end with 6 cohorts for a total of 60 patients treated with Coartem, the power to detect treatment difference using 2-sided test at the 5% significance level is 76% and 94% for n=10 and 20 patients treated with KAE609, respectively, if the true rate is 40% for KAE609 and 5% for the Coartem.

